### 23.1 ATTACHMENT 1: SUBJECT'S SATISFACTION QUESTIONNAIRE

#### Subject Satisfaction Questionnaire

Please circle the most appropriate answer for each question according to the following scale:

1. Strongly disagree
2. Disagree
3. Neither agree or disagree
4. Agree
5. Strongly agree

Space is provided for comments.

Scale

1. I have not experienced any inconvenience during the C-Scan procedure. If 1 or 2 are given, please explain:	1 2 3 4 5
2. I have not experienced any pain during the C-Scan procedure. If 1 or 2 are given, please explain:	1 2 3 4 5
3. I did not need any analgesic or other pain medication during the C-Scan procedure. If 1 or 2 are given, please explain:	1 2 3 4 5
4. I have not experienced any inconvenience while ingesting the contrast media 3 times a day If 1 or 2 are given, please explain:	1 2 3 4 5
5. I Would recommend the C-Scan procedure for colonic screening If 1 or 2 are given, please explain:	1 2 3 4 5
6. The C-Scan procedure didn't affect my daily routine If 1 or 2 are given, please explain:	1 2 3 4 5
7. I have not experienced any inconvenience during capsule excursion If 4 or 5 are given, please specify:	1 2 3 4 5
8. Do you have any additional comments regarding the C-Scan procedure?	

CONFIDENTIAL

	Document Title	Clinical Investigational Plan For Study CL-SY-02-0096		
	Document No.	DOC001593	Revision	03

## 23.2 ATTACHMENT 3: SUBJECT'S SATISFACTION QUESTIONNAIRE-COLONOSCOPY

### Subject Satisfaction Questionnaire

Please circle the most appropriate answer for each question according to the following scale:

1. Strongly disagree
2. Disagree
3. Neither agree or disagree
4. Agree
5. Strongly agree

Space is provided for comments.

Scale

1. I have not experienced any inconvenience during the Colonoscopy procedure. Please explain:	1 2 3 4 5
2. I have not experienced any pain during the Colonoscopy procedure. Please explain:	1 2 3 4 5
3. I did not need any analgesic or other pain medication during the Colonoscopy procedure. Please explain:	1 2 3 4 5
4. The C-scan procedure was easier for me compare to the Colonoscopy procedure Please explain:	1 2 3 4 5
5. For my next colonic screening I will prefer the C-Scan procedure Please explain:	1 2 3 4 5
6. Please specify the advantages of the C-Scan ver. Colonoscopy in your opinion:	
7. Do you have any additional comments regarding the C-Scan procedure?

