### 10.4 Secondary Outcome Measures

- Subject compliance will be assessed by
  - Non-compliance rate throughout the study via diary completion by the subject Specific questionnaire completed by remote subject monitoring (via telephone)
- Subject satisfaction will be established by:
  - Designated questionnaire that focuses on patient's impressions regarding tolerance and potential safety concerns. Acceptance criteria was defined as average score >3.5 (1- low satisfaction to 5- high satisfaction), which represent high satisfaction with the safety and tolerance of the C-scan system.
  - Comparing patient's satisfaction with colonoscopy procedure.
- Collecting procedure related data:
  - Technical performance in normal daily routine.
  - Segmental transit time.
  - Procedure duration.
  - Bowel movements.
  - Agreement between C-Scan and colonoscopy with respect to the presence/absence of colonic polyp(s) [Note: C-scan data not to be used for clinical decision making in the care of patients, for this clinical study].
  - Inter-observer variability in the detection of significant clinical findings on a 'per patient' decision
- Battery life Assessment
  - Assessing adequate power supply for complete scan of the colon: length of capsule operation lifetime with respect to the lifetime specification of 100 +/- 10% hours.
- Device performance
  - Assessing colon model by the physician reviewers as presented on C-Scan View (e.g., normal, partial, right side missing, etc.).
  - Collecting data to improve the product's algorithm.

	Document Title	Clinical Investigational Plan For Study CL-SY-02-0096		
	Document No.	DOC001593	Revision	03

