### **13.8 Follow-Up 3: Post-Colonoscopy Procedure**

Subject will be telephoned by study site to assess subject satisfaction with the colonoscopy procedure as compared to the C-Scan. Follow up window is 1-3 days post-colonoscopy. Additionally, the BBPS and colonoscopy report will be collected from the test site for comparative analysis with the C-Scan procedure. The subject will be exited from the study upon completion of this follow-up

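### All three comparative items on the colonoscopy questionnaire are framed towards C-Scan, so stated ease and preference are at risk of bias in its favour

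*Combined protocol and SAP*

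**What the plan says.** Protocol section 10.4 lists, under subject satisfaction, the outcome "Comparing patient's satisfaction with colonoscopy procedure". Section 13.8 describes how it is obtained, one to three days after colonoscopy: "Subject will be telephoned by study site to assess subject satisfaction with the colonoscopy procedure as compared to the C-Scan".

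The form is in section 23.2 (Attachment 3). It has five items rated from 1 (strongly disagree) to 5 (strongly agree), with a neutral midpoint, and two free-text items:

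- Items 1 to 3 rate colonoscopy alone, for example "I have not experienced any pain during the Colonoscopy procedure".
- Item 4: "The C-scan procedure was easier for me compare to the Colonoscopy procedure".
- Item 5: "For my next colonic screening I will prefer the C-Scan procedure".
- Item 6 (free text): "Please specify the advantages of the C-Scan ver. Colonoscopy in your opinion".
- Item 7 (free text): "Do you have any additional comments regarding the C-Scan procedure".

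Each rated item also has an undirected request to explain. Section 14.1.4 plans descriptive statistics only. No scoring rule or threshold is given for items 4 and 5.

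**The concern.** Some respondents tend to agree with whatever statement is put to them. When every comparative statement favours the same procedure, that tendency raises the apparent result for that procedure and no reversed item pulls it back. Item 6 adds to this by presupposing that C-Scan has advantages, without asking for its drawbacks or for any advantage of colonoscopy.

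Items 4 and 5 are the only rated items that ask directly about relative ease and preference. The clinical investigation summary (section 4) says the device is intended partly for people who decline colonoscopy, so a preference percentage from this study may well be quoted. A descriptive analysis reports the percentage as collected and cannot remove an effect of wording.

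**Working it through.** The plan states no preference figure and no derivation for one, so there is nothing to reproduce. The check is a count of wording direction, followed by an illustration of size under a stated assumption.

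**Step 1: direction of each Attachment 3 item**

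| Item | Type | Direction |
|---|---|---|
| 1–3 | rated, colonoscopy alone | favourable to colonoscopy; same wording as items 1–3 of the C-Scan form (section 23.1) |
| 4 | rated, comparative | towards C-Scan |
| 5 | rated, comparative | towards C-Scan |
| 6 | free text, comparative | towards C-Scan |
| 7 | free text, C-Scan only | open |

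Of the three comparative items (4, 5 and 6), three point towards C-Scan and none towards colonoscopy.

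**Step 2: possible size (assumed rate, not from the documents)**

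Let p be the true share who prefer C-Scan, and a the share of all other subjects who agree anyway. The other subjects include those with no preference and those who prefer colonoscopy. Then

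observed agreement = p + a(1 − p).

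With a assumed at 10% to 20%:

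- p = 50%: 0.50 + 0.10 × 0.50 = 55%; 0.50 + 0.20 × 0.50 = 60%.
- p = 40%: 0.40 + 0.10 × 0.60 = 46%; 0.40 + 0.20 × 0.60 = 52%.

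For a true 40% to read as a majority requires 0.40 + 0.60a > 0.50, so a > 0.10/0.60 = 16.7%. Only the upper third of the assumed range does this.

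**Step 3: scale in this study**

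Section 14.1.1 gives up to 45 subjects. A shift of 5 to 10 percentage points is 0.05 × 45 = 2.25 to 0.10 × 45 = 4.5 subjects. The standard error of a 50% proportion is √(0.5 × 0.5/45) = 7.5 points, so the assumed shift is of the same order as sampling error.

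Take 30 of 45 (two thirds) as an arbitrary example of a result that would look like clear preference. The exact binomial chance of at least 30 agreeing when the true share is 50% is:

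| Assumed a | Observed agreement | P(at least 30 of 45 agree) |
|---|---|---|
| 0% | 50% | 0.018 |
| 10% | 55% | 0.076 |
| 20% | 60% | 0.225 |

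If half of the items were worded the other way, expected agreement would be 0.5(1 − a) + 0.5a = 50% at every value of a.

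**The case against.** The strongest case on the other side has five parts.

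- **The form does not suppress complaints.** Item 7 is open, each rated item asks for an explanation, and the instructions say "Space is provided for comments". Items 1 to 6 of the C-Scan form ask for an explanation when a low score is given. This stands: a reader might infer that the free text collects only praise of C-Scan, and the form does not support that. What remains is that the only comparative free-text item is one-directional. The open prompts permit criticism in a comparison but do not ask for it.
- **Subjects can disagree.** The scale is symmetric with a neutral midpoint. This also stands against any claim that the result must favour C-Scan. A midpoint does not cancel a tendency to agree, so the risk and its direction remain.
- **The outcome is satisfaction, not preference.** Items 1 to 3 match on the two forms, each favourable to the procedure being rated, so a within-subject comparison is possible in which a tendency to agree would largely cancel. This stands and limits the impact. Those items cover inconvenience, pain and analgesia, however, not relative ease or preference, and no paired analysis is specified.
- **The illustrated rate has no source in the documents.** This stands. A reader might infer that the wording would turn a minority into a majority; that needs a rate above 16.7% at the chosen true value of 40%, and the documents give no ground for that rate.
- **Telephone collection.** A reader might infer from section 13.8 that staff read the items aloud and so add pressure to agree. The form tells subjects to circle an answer, and the schedule lists the satisfaction survey and the follow-up call on separate rows. The mode of completion is unclear, so no weight is placed on it here.

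**Conclusion.** The concern holds as a risk of bias on items 4 to 6, with a known direction and an unknown size. The direction follows from the wording alone. The range of 55% to 60% for a true 50% rests entirely on the assumption that 10% to 20% of subjects who do not prefer C-Scan agree regardless.

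Severity is minor. The affected items feed one descriptive secondary outcome in a pilot study whose primary outcome is device- or procedure-related serious adverse events. The only acceptance criterion for satisfaction, an average above 3.5 in section 10.4, is tied to C-Scan and does not govern these items. The documents do not support saying that the preference result is biased as a matter of fact, or that the whole satisfaction comparison is compromised.

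**What to change.** Before the form is first used:

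1. Replace items 4 and 5 with two-sided five-point items: 'Which procedure was easier for you?' and 'Which would you choose next time?', each running from 'colonoscopy, clearly' through 'no difference' to 'C-Scan, clearly'.
2. Change item 6 to ask for the advantages and the disadvantages of each procedure.

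The cost is one revised page and an IRB notification. The preference figure may become less favourable to C-Scan. The change has to come before data collection, because the effect of one-directional wording cannot be separated from true preference afterwards.
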